Cover Page

**Official title: „Randomised cross-over Study
on the Effectiveness of Elaboration and
Proactive Feedback as Part of Formative Key
Feature Examinations in Undergraduate
Medical Education“**

NCT number: not yet assigned

Document date: 28/8/2018

Trial Protocol

Title:

„Randomised cross-over Study
on the Effectiveness of Elaboration and
Proactive Feedback as Part of Formative Key
Feature Examinations in Undergraduate
Medical Education“

Project Lead:
[name]. med. [name]
Division of Medical Education Research and Curriculum Development
University Medical Centre Göttingen

There is no third-party funding or support for this trial.

1. Study aim

Repeated formative (i.e., non-graded) testing enhances student learning outcome on clinical reasoning skills. At University Medical Centre Göttingen (UMG), a number of trials investigating the so-called *testing effect* have already been conducted in the past. They showed, amongst others, that dealing with videotaped clinical cases compared with written cases increases short-term outcome but not long-term retention. More recently, one study addressed the question whether clinical reasoning skills can be fostered by an elaboration of incorrect answers. Results of a previous trial had suggested that a considerable number of students were not sufficiently motivated to provide thorough answers to elaboration questions. This impression remained even after introducing financial incentives for students although a small but significant effect of the intervention was noted (percent score in the exit exam: $65.7 \pm 19.6\%$ vs. $62.3 \pm 22.9\%$; $p = 0.022$). Yet, student performance remained moderate at best. Thus, the intervention will now be extended by including automated feedback provided by email. All students participating in an electronic case-based seminar (e-seminar) will receive an individual email after the event, displaying their raw point score as well as their written answers to elaboration questions and expert comments reflecting current medical knowledge.

This trial addresses the following research question:

What is the effect of elaboration and consecutive automated and individual feedback following e-seminars on medical students' clinical reasoning skills?

2. Background and previous work

According to recent findings, retrieval of knowledge is not a passive process. Instead, long-term retention is being facilitated by the act of retrieval itself (‘retrieval hypothesis’). Potentially, this effect that has also been called ‘direct testing effect’, could also be due to additional exposure to the content during an assessment. However, complex studies in which exposure was experimentally controlled did not lend support to this ‘total time hypothesis’. The effectiveness of examinations as memory boosters with respect to medical education has been shown in a number of studies. However, many of these used short follow-up periods (e.g., 7 days) or implemented reproduction tests on a low taxonomic level. Yet, these studies suggest that formative examinations may promote learning processes. According to a review of the topic, these exams should contain production tests and be repeated with appropriate spacing. In addition, students should receive feedback shortly after the exam.

Given these recommendations, longitudinal key feature examinations were implemented in three consecutive teaching modules at our institution in 2013. These case-based examinations lend themselves to fostering complex cognitive skills. A key feature is defined as a critical step in solving a clinical problem. According to this definition, a key feature case consists of a case vignette and approximately five consecutive questions relating to the diagnostic and therapeutic approach. In contrast to single-best answer multiple choice questions, students cannot choose from a list of five answer options but must produce a written answer. Thus, rather than recognizing the correct answer, the aim of a key feature examination is to actively produce a correct answer. In order to save students from making follow-on mistakes, they are informed about the correct answers to preceding questions whenever attempting to answer the next question. At this point, students also receive static feedback on their previous answer.

Recently, the results of a randomized cross-over trial comparing active retrieval using key feature questions with repeated study of the same material were published. The data showed that working on key feature cases with static feedback elicited a larger medium-term learning

outcome than passive restudying of the same content. The specific role of the feedback in the process however remained unclear.

Current findings from educational psychology research suggest that diagnostic errors made in a protected learning environment can serve as starting points for further elaboration which may eventually lead to a reduction in diagnostic errors in clinical practice. This trial aims to implement and evaluate this concept. To this end, existing data obtained in previous trials at UMG were analysed with regard to common clinical reasoning errors (CCRE). On this basis, e-seminars running in parallel to curricular teaching in the three aforementioned modules were modified in that – upon answering specific questions – students were prompted to comment on frequent CCREs ('elaboration'). The analyses of student entries revealed that despite all the content having been covered in preceding teaching sessions, a considerable proportion of entries represented slack answers (e.g., 'don't know' or 'no idea'), suggesting that students might not have taken the exercise serious enough. In fact, this notion was corroborated in student comments during focus group discussions following the main study. As a consequence, the study was repeated in the following year, and this time complete answers to elaborations questions were incentivised using book vouchers. In this setting, a significant effect of the intervention was noted but student performance was still at best moderate. Given the importance of feedback for learning processes elicited by formative examinations, this aspect will be strengthened in the trial described here. Students can already open a text box containing static feedback after each question, but so far they have not received personal feedback after each exam. In winter term 2018/19, all students participating in the trial will receive individual emails containing (a) the raw point score achieved in each e-seminar, (b) static expert feedback to elaboration questions, and (c) their own entries to these elaboration questions. Thus, students will be able to compare their own answers to the instructor feedback.

3. Design and Conduct of the Study

This is a randomised controlled cross-over educational trial. Participating students will be stratified according to sex and summative exam scores in the previous term. Subsequently, they will be randomized to one of two study groups in a 1:1 fashion. During weekly e-seminars, they work on clinical cases addressing diagnostic and therapeutic strategies needed to manage patients with prevalent symptoms of general medical disorders. Cases will be presented as key feature cases with five questions per case. For some of these questions, elaboration questions will be written. These will focus on common misperceptions and clinical reasoning errors. When used as 'intervention items', elaboration questions will be shown after the original key feature question. Students will be prompted to enter a free-text answer. Upon completing both the original item and the elaboration question, they will be able to access a static feedback ('expert comment'). This feedback will be included in an email sent to all students on the day after the e-seminar, also containing individual performance data as well as the student's free-text answer to the elaboration question. When used as a 'control item', the same key feature question is being displayed, and students can access the expert comment directly after answering the question. Information on control items will not be contained in the mailed feedback. Every student will be exposed to 15 intervention and control items, respectively, and each of these will be shown twice over the course of 10 weeks. Items that are being shown as intervention items in one randomized group will be shown as control items in the other group and vice versa, thus making each student their own control. At the end of the study, individual 'intervention item' and 'control item' scores will be computed for each student, and these two scores will be compared using a paired t Test. This primary analysis will be done to test the following hypothesis:

„Long-term retention will be better for content that has been repeatedly tested with additional elaboration questions and subsequent mailed individual feedback than for content that has been repeatedly tested alone.“

Long-term retention will be assessed in a formative electronic key feature assessment in summer term 2019. It will be identical to the entry and exit exam held in winter term 2018/19.

Secondary analyses will include unadjusted and adjusted linear regressions with percent scores in the exit exam and retention test as dependent variables and student characteristics as well as their engagement with key feature questions as independent variables.

4. Enrolment

Before the beginning of winter term 2018/19, all students enrolled to the three modules will receive an email describing the study. Particular emphasis will be put on the fact that study participation is voluntary. Students will be invited to participate in the trial. In this context, participation means that students agree to having their data analysed for the purpose of the trial. Every student will receive teaching and will also be invited to take e-seminars regardless of study participation. Written consent will be obtained in a classroom session on the first day of the module.

5. Archiving and Data Protection

For communication purposes, student names and email addresses need to be known. For each student providing written consent, these data as well as exam scores achieved in the preceding term will be provided by the Study Deanery. Personal data will be stored on a desktop computer to which only the Project Lead has access.

During e-seminars, students log onto the system using their individual credentials. Output files of the key feature examination system contain student login names. These will be used to merge files from various sources. Following the merging procedure and before running any analyses, all personal data will be deleted from the dataset. As a consequence, no individual student can be identified in this final dataset.

Responsibility for data treatment and storage lies with the Project Lead.

The Trial Protocol as well as all related documents have been approved by the institution's data protection officer, [name].

Participating students are entitled to seek information on which of their personal data are being stored, and they can request all data to be deleted as long as they can still be identified in the dataset.

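### Does it matter that the protocol is unclear on whether the mailed point score counts control items?

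*Protocol*

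**What the plan says.** Section 1 (Study aim) presents the email as the new element compared with the previous trial: "the intervention will now be extended by including automated feedback provided by email". It gives the contents as "displaying their raw point score as well as their written answers to elaboration questions and expert comments reflecting current medical knowledge". It does not say which questions the score counts.

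Section 2 (Background and previous work) lists the contents again. The first is "a) the raw point score achieved in each e-seminar"; the others are the expert feedback on elaboration questions and the student's own entries.

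Section 3 (Design and Conduct of the Study) describes the email as carrying the expert comment and the free-text answer, "also containing individual performance data". It then explains that for a control item the student can open the expert comment directly after answering, and adds: "Information on control items will not be contained in the mailed feedback".

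The same section assigns every student 15 intervention and 15 control items, each shown twice over ten weeks. It compares the two item-type scores within student by a paired t test. The hypothesis sets content tested with elaboration and mailed individual feedback against content that was only tested repeatedly.

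**The concern.** The three sections describe one part of the email in three ways, and the most specific description (a score per e-seminar) does not fit the most categorical statement (nothing on control items is mailed). If the score is a seminar total, control-item points enter it, and it reaches the student once, for both item types together.

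That seems to matter because the email is what this trial adds. Section 1 motivates it by the level of performance in the previous trial: "Yet, student performance remained moderate at best". If the score raises effort in general, performance on both item types may rise while the difference between them stays the same. The primary contrast would not show this gain, and a reader might conclude that the mailing achieved nothing. It might also be said that control content was then not purely tested alone, and that the email could not be reproduced from the text.

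**Working it through.** The protocol states no sample size, power or effect size that bears on this point, so the check is a comparison of the sections plus some simple algebra.

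**1. Would a seminar total include control items?** Section 3 gives 15 control items × 2 showings = 30 control showings per student in ten weeks. With one e-seminar in each of the ten weeks (assumed from the weekly schedule), that is 30 / 10 = 3 per seminar on average. Intervention items give the same figure. A seminar total would therefore normally contain control-item points, and the literal tension is real.

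**2. Is the scope of the score undefined?** Not entirely. Section 2 ties the score to the e-seminar. The phrases in Sections 1 and 3 are shorter references to the same component, and neither restricts it to intervention items.

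**3. What does the exclusion sentence cover?** It comes directly after the sentence on how students reach the expert comment for a control item. It contrasts with the description of the intervention item, whose expert comment and free-text answer are mailed. Read there, it says that no such content is mailed for control items. A single total does not tell a student which control item was right or wrong, or why, so it is compatible with that reading.

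**4. What happens to the primary contrast?** Let m be a student's mean without the intervention, d the effect specific to intervention items (elaboration, mailed answer, mailed comment), s the effect of the score on intervention items, and r the fraction of s that also reaches control items. Assume that the effects add.

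- Intervention-item mean: m + d + s
- Control-item mean: m + rs
- Difference: d + s(1 − r)

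With r = 1 the difference is d; with r = 0 it is d + s. For s of zero or more and r between 0 and 1, the score adds nothing or adds part of its own effect. If d and s are both zero, the difference is zero, so the test is not biased under the null hypothesis.

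**5. Does the scope of the score determine r?** No. The number of control items counted in the score and the fraction of its effect that reaches control content are different quantities. A total may motivate a student equally for both item types whatever the share of control points in it. A score restricted to intervention items could do the same, because motivation belongs to the student and not to the item. Settling the scope would therefore not settle the attribution.

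**6. Can the effect be sized?** The previous trial's exit-exam difference was 65.7 − 62.3 = 3.4 percentage points. Adding an assumed common lift of 5 points to both means gives 70.7 − 67.3 = 3.4. This only confirms that a constant cancels in a difference. The protocol supplies neither s nor r, so any figure for the lost effect would be an assumption.

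**The case for a change.** The strongest case for a change is that the content of the intervention, and what is withheld from the control condition, belongs in the protocol and cannot be left to the SAP. On a literal reading, Sections 2 and 3 cannot both hold for a seminar that contains control items. Aligning them would cost a few sentences and leave the conduct of the trial untouched. Describing the contrast as elaboration plus item-specific mailed feedback, and showing both item-type means beside their difference, would make a common lift visible and guard against the wrong conclusion about the mailing.

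The literal tension stands, and a clarifying clause would do no harm. The rest carries less weight:

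- The hypothesis is about a package applied to content, and the research question in Section 1 likewise joins elaboration and feedback. No condition has elaboration without the email, so the design could not separate the mailing's contribution however the score were defined.
- Concluding that the mailing added nothing would require a comparison with the previous cohort. That comparison is not randomised, and the protocol does not plan it.
- Section 3 already computes an intervention-item and a control-item score for each student. Showing both means is a matter for the report.
- The layout of the email is operational detail, and Section 2 lists its contents well enough to build it.

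**Conclusion.** No change to the plan is called for. The two descriptions of the score fit together once the exclusion is read as referring to item-level feedback, which is what its context suggests. Followed as written, the plan gives a valid within-student comparison for elaboration plus the feedback mailed on specific items.

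The one real limit is attribution: a general effect of the score shared by both item types is not visible in the difference. That limit comes from using each student as their own control, a fair trade-off, and no rewording of the score's scope would remove it. Its size cannot be derived from the protocol.

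This conclusion assumes that the score acts additively and no more strongly on control than on intervention content, and that control items are distinguished by item rather than by seminar, as Section 3 describes. Under either reading of the score, the mailing, the items, the sample and the paired test remain the same.

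### The primary paired t test ignores the randomised group, so any difficulty gap between the two 15-item sets is counted as error and costs power; unequal groups would also shift the estimate

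*Protocol*

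**What the plan says.** The design and the primary test are both in Section 3, Design and Conduct of the Study. Students are stratified by sex and previous exam score, and then "they will be randomized to one of two study groups in a 1:1 fashion". On the items: "Every student will be exposed to 15 intervention and control items, respectively". The sets are exchanged between groups: "Items that are being shown as intervention items in one randomized group will be shown as control items in the other group and vice versa". The protocol presents this exchange as the reason each student can serve as their own control.

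Each student then receives one intervention-item score and one control-item score, and "these two scores will be compared using a paired t Test". The status of this test is explicit: "This primary analysis will be done to test the following hypothesis". The outcome is long-term retention, measured in summer term 2019, the term after the intervention.

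The protocol does not say that the two item sets are matched on difficulty. The secondary regressions at the end of Section 3 take "student characteristics as well as their engagement with key feature questions as independent variables"; randomised group is not named.

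**The concern.** Being their own control removes differences in ability between students. It does not remove differences between items, because each student meets a given item under one condition only. The randomised group decides which set is the intervention set, so it decides the sign with which any difficulty gap enters a student's difference.

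Exchanging the sets cancels the gap from the overall mean when the analysed groups are equal in size. It never cancels the gap from the spread of the differences, and a one-sample test of pooled differences uses that spread as its error term. A known, design-created source of variation is therefore treated as noise.

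Power is what is mainly at stake. Section 1 describes the earlier trial by saying "a small but significant effect of the intervention was noted": 65.7% against 62.3%, p = 0.022. A follow-on trial looking for an effect of that order can ill afford avoidable noise. A second, smaller issue is that the retention test comes a term later, so the groups analysed need not still be 1:1, and part of the gap can then enter the estimate itself.

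**Working it through.** The protocol gives no sample size, power or SD for this trial, so there is no design figure to reproduce. The check is algebra, followed by a range of assumed inputs.

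**Model.** For student i, difference d = intervention score − control score = τ + gδ + e, where g = +1 or −1 by group, δ is the difficulty gap between the sets, and e has SD s.

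- Paired test: expected mean = τ + δ(n1−n2)/N; variance used = s² + δ²[1 − ((n1−n2)/N)²], which is s² + δ² at 1:1.
- Group in the model: estimate = average of the two group means, expectation τ whatever the group sizes; residual variance s².

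**Inputs.**

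- Effect: 65.7 − 62.3 = 3.4 points (Section 1), used as a scale only.
- SD: if p = 0.022 came from a paired t test, SD = (3.4/t)√N. N = 60: t = 2.353, SD = 11.2. N = 100: t = 2.327, SD = 14.6. N = 150: t = 2.315, SD = 18.0. I use s = 12, 15 and 18.
- Gap: with an assumed item-difficulty SD of 20 points and 30 items split at random, the SD of the gap is 20√(1/15 + 1/15) = 7.3, and the median absolute gap is 0.6745 × 7.3 = 4.9. I use δ = 2, 4.9, 7.3 and 10.
- N = 100 at the retention test, two-sided α = 0.05 (both assumed).

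**Power at 50:50, τ = 3.4 (simulation, 40,000 runs per cell).**

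| s | δ = 2 | δ = 4.9 | δ = 7.3 | δ = 10 | Group in model |
|---|---|---|---|---|---|
| 12 | 79% | 75% | 69% | 60% | 80% |
| 15 | 60% | 57% | 52% | 46% | 61% |
| 18 | 46% | 44% | 40% | 36% | 46% |

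The first four result columns are the paired test. With no true effect and s = 12, it rejects 4.7%, 3.3%, 2.2% and 1.0% of the time across those columns; the group model stays at about 5%.

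**Inflation of the reported variance, δ²/s², at δ = 4.9.** 24.0/144 = 17%, 24.0/225 = 11%, 24.0/324 = 7%. This is the extra sample needed for the same reported standard error. For the same power at s = 12 the figure is about 11 to 12%, because at 50:50 the true sampling variance of the mean is unchanged and only the reported one is inflated.

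**Unequal groups.** At 55:45, (n1−n2)/N = 0.10, so the shift is 0.5, 0.7 and 1.0 points for δ = 4.9, 7.3 and 10. Type I error there is 4% to 5%.

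**How likely imbalance is.** If 100 students remain of about 125, 150 or 200 and dropout does not depend on group, a split of 55:45 or worse has probability 5%, 12% or 20%; 60:40 or worse is under 1%. Averaged over such dropout, the paired test's type I error is 1.6% to 4.4% and its mean bias is about zero. Clear inflation needs a marked split: at 72:48 with s = 15, type I error is 9% for δ = 5 and 19% for δ = 10.

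**The case against.** The strongest reply is that the planned test is valid. At 1:1 the estimate is unbiased and the test errs on the safe side, so this is a matter of efficiency and the protocol contradicts nothing. That is right about validity and limits the point accordingly. It does not remove it: the test is fixed in the protocol as the primary analysis, and its inefficiency follows from the protocol's own design.

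The size is also open to challenge, and much of this stands.

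- δ is not in the protocol. Random splitting is no better documented than matching, and at δ near zero nothing is lost.
- If the earlier trial also swapped sets, its SD already contains δ². At N = 100, removing a gap of 4.9 gives s = √(14.6² − 4.9²) = 13.8 instead of 14.6. The power table is therefore a comparison of two tests, not a forecast.
- The s = 12 row, with the largest losses, corresponds to an earlier trial of about 70 students, not 100.
- The 3.4 points come from an exit exam without mailed feedback, whereas this trial's outcome is retention with feedback added.
- The shift under imbalance averages to zero over chance dropout, and nothing in the protocol suggests that dropout will differ by group.
- The secondary regressions model scores, not the within-student difference, so the absence of group there is only weak supporting evidence.

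**Conclusion.** The concern holds and should be fixed; it is not fatal. That the gap inflates the error variance at 1:1, and shifts the estimate when the groups are unequal, follows directly from the stated design. How much this matters depends on δ, s and N, none of which the protocol gives.

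Under the assumptions above, the power loss is negligible for well-matched sets, modest at the median gap under random splitting, and substantial at a gap of 10 points. The loss of power is the main consequence. The shift is secondary: at 55:45 with δ = 10 it is 1.0 point, about 30% of the earlier 3.4-point effect (1.0/3.4), but such imbalance would usually arise by chance and in either direction. A false-positive problem arises only with a marked imbalance such as 60:40, which chance dropout makes very unlikely.

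**What to change.** Replace the paired t test in Section 3 with a linear regression of each student's intervention-minus-control difference on randomised group coded +1/−1, and test the intercept. The intercept is the equally weighted mean of the two group means, judged against within-group residual variance; this is the standard analysis of a two-sequence cross-over. Sex and previous exam score, already used for stratification, may be added as centred covariates. The change should be specified before the retention data are analysed.

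The cost is one sentence and one degree of freedom, with no new data. If the sets turn out equally difficult and the groups unequal, the standard error grows by the factor 1/√(4f(1−f)), where f is the share of students in one group: 1/√(4 × 0.55 × 0.45) = 1.005 at 55:45 and 1/√(4 × 0.60 × 0.40) = 1.021 at 60:40, that is 0.5% and 2.1%.

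### The primary paired t test is valid but inefficient: it uses neither the same-item entry exam nor the randomised group

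*Protocol*

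**What the plan says.** Section 3 (Design and Conduct of the Study) computes two scores per student at the end of the study, one for intervention items and one for control items, and states that "these two scores will be compared using a paired t Test". It gives this test primary status: "This primary analysis will be done to test the following hypothesis", the hypothesis being about long-term retention measured in summer term 2019.

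The same section describes two further pieces of information:

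- On the retention test: "It will be identical to the entry and exit exam held in winter term 2018/19". Each student who sat the entry exam therefore has a pre-intervention score on the same items.
- On the design: "Items that are being shown as intervention items in one randomized group will be shown as control items in the other group and vice versa". Group membership therefore decides which item set carries the intervention.

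The regressions at the end of Section 3 are secondary. They list "student characteristics as well as their engagement with key feature questions as independent variables" and name neither the entry exam nor the randomised group. Section 5 says of the login names in the output files: "These will be used to merge files from various sources". Section 1 quotes one earlier result, where "a small but significant effect of the intervention was noted": 65.7% against 62.3% in the exit exam, p = 0.022.

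**The concern.** The protocol itself chooses the primary test, so this is not a detail left to an analysis plan. Student ability cancels within the pair, but two other sources of variation remain.

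The first is item-specific prior knowledge. A student may already know more of one item set than of the other. The entry exam measures this on the same items, and the t test does not use it.

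The second is item-set difficulty. Let g be the difficulty gap between the two sets. The expected student difference is effect + g in one group and effect - g in the other. With equal groups the gap cancels from the mean, but it stays in the SD of the differences. The reported standard error is then too large and the test is conservative. With unequal analysed groups the gap no longer cancels, and the estimate shifts. Unequal attendance at the summer test would produce this.

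The only earlier effect quoted is 3.4 points, and it comes from the exit exam rather than a later retention test. Precision therefore matters here.

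**Working it through.** The protocol states no sample size, power, alpha or drop-out rate, so there is no figure of its own to reproduce.

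**Anchor from Section 1.** The effect is 65.7 - 62.3 = 3.4 points. For p = 0.022 (two-sided assumed), z = 2.29, so SE = 3.4/2.29 = 1.48. Using t quantiles for any assumed N from 60 to 250 gives 1.445 to 1.475, so this figure hardly depends on N. At N = 120 the implied SD of the paired difference is 1.465 × √120 = 16.05, which is why 16 is used below.

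**Entry difference.** Adjusted SE = 1.48 × √(1 - rho²), and power for 3.4 points = Φ(3.4/SE - 1.96). Rho is assumed.

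| rho | variance | SE | power |
|---|---|---|---|
| 0 (unadjusted) | – | 1.48 | 63% |
| 0.1 | -1% | 1.48 | 63% |
| 0.2 | -4% | 1.45 | 65% |
| 0.3 | -9% | 1.42 | 67% |
| 0.4 | -16% | 1.36 | 71% |
| 0.5 | -25% | 1.29 | 75% |

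**Group term, equal groups (assumed 60/60, SD 16).** The t-test SE is √((16² + g²)/120), and with a group term it is 16/√120 = 1.46 at any g.

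- g = 4: √(272/120) = 1.51 (1.50 in simulation); variance up by 16/256 = 6%.
- g = 8: √(320/120) = 1.63; variance up by 64/256 = 25%.

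**Group term, unequal groups (assumed 66/54).** The t-test estimate shifts by g × (66 - 54)/120 = 0.1g, that is 0.4 points at g = 4 and 0.8 at g = 8. With the group term the shift is about 0.

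**Simulation of both terms together.** Settings: 6,000 runs each, 120 students, SD of the retention difference 16 and of the entry difference 12, effect 3.4.

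- Rho 0.3, equal groups: power of the t test against the proposed model is 0.61 against 0.68 at g = 4. At g = 8 it is 0.54 to 0.56 over repeated simulations, against 0.68.
- No gap, rho 0: SE 1.455 against 1.461. This is the whole price when there is nothing to gain.
- No gap, no missing entry exams: coverage of the proposed model is 94.6% to 95.2%.

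**Error rate of the t test under no effect (assumed N = 100, within-group SD 15).** At 50:50 it is 5.5%, 4.2%, 1.8% and 0.7% for g = 0, 5, 10 and 15. At 55:45 it stays at or below about 5%. At 60:40 it is 8.6%, 15.1% and 21.4% for g = 5, 10 and 15. The group term holds it near 5% throughout.

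**Missing entry exams (group-mean imputation).** Empirical SE, t test against proposed model:

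| missing | rho 0.2 | rho 0.3 | rho 0.5 |
|---|---|---|---|
| 20% | 1.44 vs 1.44 | 1.46 vs 1.41 | 1.49 vs 1.34 |
| 30% | 1.46 vs 1.47 | 1.45 vs 1.42 | 1.46 vs 1.37 |

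**The case against.** A paired t test in a mirrored design is a standard and valid choice, and replacing it may look like preference. Rho, the item-set gap and the sample size are all absent from the protocol. The entry gain may be negligible: at rho 0.1 power does not move, and at rho 0.2 with 20% of entry exams missing nothing is gained. Low entry scores would also limit rho. If 20% of items are right at entry and 60% at retention (both assumed), the largest possible single-item correlation is √(0.2 × 0.4/(0.8 × 0.6)) = 0.41; at 10% and 60% it is 0.27. The 63% baseline merely restates another trial's p value. At 66/54 the t test's error rate is close to nominal despite the shift. A covariate model can also be mis-specified, which the t test cannot.

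Much of this stands. The upper rows for rho are optimistic, although the single-item ceiling does not strictly bound the correlation of differences between 15-item averages. The power figures serve only to compare analyses and do not predict this trial's power. Serious harm to the error rate needs clearly unequal groups and a real gap, and neither is documented. None of this defends leaving both terms out, because including them costs almost nothing when they do not help. The risk of mis-specification is real and is met by stating the model exactly.

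**Conclusion.** The point holds as one of efficiency, with some protection of the estimate. The fixed primary test is not invalid, and no result would be wrong merely because it was used with near-equal groups. It gives up precision that data already collected would supply. The size rests on assumptions:

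- **Entry difference:** between nothing and about a quarter of the variance, more plausibly the lower part of that range if entry scores are near the floor.
- **Group term:** nothing if the item sets are equally hard; 6% or 25% of variance at gaps of 4 or 8 points. It also removes a shift of one tenth of the gap at 66/54.

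The group term has the firmer basis, because it follows directly from the mirrored design. The change should be made, but the trial does not stand or fall by it.

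**What to change.** Define the primary analysis as a linear regression of each student's retention difference (intervention minus control) on the entry-exam difference for the same items and on randomised group coded +1/-1. The intercept is the treatment effect. Keep the paired t test as a sensitivity analysis.

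Two details need to be written down:

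- Enter the entry difference uncentred. Its expectation averaged over the two groups is zero by randomisation, and the group term absorbs any item-set gap at entry. Centring it within group must be avoided: the estimate then gains no precision while its model SE shrinks. At rho 0.5 with no effect, simulation gave an empirical SE of 1.45 against a model SE of 1.26, and a type I error of about 9%.
- For a missing entry exam, impute the mean entry difference of the student's randomised group, without a missing indicator, so that these students still inform the intercept.

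The cost is protocol or SAP wording and the loss of two degrees of freedom. No new data are needed, because the entry exam is already held and login names link the files. Entry-exam item scores and group must be in the merged file before personal data are deleted. The gain shrinks as entry exams go missing. At 30% missing it is nil for rho 0.2, and at rho 0.5 the model SE is slightly too small (1.34 against 1.37 empirical, coverage 94.6%).
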